7.8.3 Follow-up period

During the follow-up period, subjects who require a repeat ACTH-challenge test at FU2 (Section 6.1.5) should not receive corticosteroid therapy (topical or systemic), enzymatic inductors, cytochrome P450 inhibitors, hypoglycemic sulfonamides, anti-depressive medications, estrogen therapy, or any other medication known to affect cortisol levels/HPA axis integrity. Such subjects should also continue to use contraception if they are of child-bearing potential.

Note that treatment with Enstilar[®] or IP is not allowed during the follow-up period (Section 6.1.5).

7.9 Discontinuation

Subjects **may** withdraw from the trial for any of the following reasons:

1. *Screening failure*
2. *Lack of efficacy:* The (sub)investigator is free to withdraw the subject at any time based on a medical judgement.

3. *Adverse event (please specify):* Any adverse event (AE) that the (sub)investigator considers unacceptable.
4. *Withdrawal by subject:* Subjects are free to withdraw from the clinical trial at any time and for any reason.
5. *Lost to follow-up*
6. *Death*
7. *Other (please specify):* Other reasons than stated above which require the subject to (be) withdraw(n) should be specified.

Subjects **must** be withdrawn from the trial for any of the following reasons:

8. *Subjects who do not achieve treatment success (PGA score of 'clear' or 'almost clear' with at least a 2-grade improvement from baseline) after initial 4-week treatment*
9. *Subjects who are not scored as 'clear' or 'almost clear' after 4-week treatment of relapse*

If adverse event or other is selected, a specification must be supplied.

Subjects who are discovered, after enrolment/randomisation, not to have fulfilled all in-/exclusion criteria at the time of enrolment should discontinue treatment unless the (sub)investigator, based on clinical and ethical evaluation, finds discontinuation inappropriate.

The final efficacy assessment (at the correct scheduled time) should be attempted to be completed for all subjects. Such deviation(s) from the (Consolidated) Clinical Trial Protocol must be reported to LEO Pharma A/S (and Independent Ethics Committee (IEC)/Institutional Review Board (IRB), as appropriate) and recorded in the Clinical Study Report.

Reason(s) for discontinuation from trial will be recorded in the eCRF. Subjects withdrawn will not be substituted.

8 Trial Schedule and Assessments

8.1 Schedule of Trial Procedures

The schedule of trial procedures is shown in [Table 4](#).

Table 4: Schedule of Trial Procedures

	Screening	Open-label phase 4 wks	Maintenance phase					Follow-up phase				
			Visit 1 ²⁾ Baseline	Visit 2 Randomisation	V3 to V14	V15	UNS/ Relapse FU visit ¹⁷⁾	Early Withdrawal	FU1 ^{18,20)}	FU2 ^{19,20)}	FU3 ²¹⁾	UNS FU ²²⁾
Frequency			Every 4 weeks (from V1 to V15) relative to V2								8 weeks after V15/EW	As needed
Visit window			±4 days (from V1 to V15)				No more than 7 days after subject calls		±2 days	±4 days	±4 days	≤ 7 days after call
Informed consent ³⁾	X											
Informed consent for biomarkers ³⁾	X											
Informed consent for ACTH challenge tests ³⁾	X											
Informed consent for photographs ³⁾	X											
Inclusion/Exclusion criteria	X	X										
Demographics	X											
Fitzpatrick Skin type	X											
Height and weight	X											
Vital signs (BP, pulse)		X	X		X		X					
Physical examination	X		X ⁴⁾		X		X			X ²⁵⁾		
Medical history/locations of psoriasis	X											

	Screening	Open-label phase 4 wks	Maintenance phase					Follow-up phase				
			Visit 1 ²⁾ Baseline	Visit 2 Randomisation	V3 to V14	V15	UNS/ Relapse FU visit ¹⁷⁾	Early Withdrawal	FU1 ^{18,20)}	FU2 ^{19,20)}	FU3 ²¹⁾	UNS FU ²²⁾
Frequency			Every 4 weeks (from V1 to V15) relative to V2								8 weeks after V15/EW	As needed
Visit window			±4 days (from V1 to V15)				No more than 7 days after subject calls		±2 days	±4 days	±4 days	≤ 7 days after call
Previous anti-psoriatic therapy	X											
Concomitant medication and procedures	X	X	X	X	X	X	X	X	X	X	X	
Pregnancy test ⁵⁾		X	X	X	X		X					
Randomisation			X									
Adverse Event ⁶⁾	X	X	X	X	X	X	X	X	X	X	X	
Laboratory: Biochemistry		X	X ⁷⁾		X ⁸⁾		X ⁸⁾	X				
Laboratory: 25-OH Vitamin D		X										
Urinalysis		X	X ⁷⁾		X ⁸⁾		X ⁸⁾	X				
Laboratory: ACTH challenge test (assigned sites only) ⁹⁾		X	X	X ¹⁰⁾	X		X ²⁴⁾		X ²³⁾			
Sampling for biomarkers ¹¹⁾		X		X ¹⁰⁾	X ¹²⁾		X ¹²⁾					
Subject's Global Assessment of disease severity		X	X	X	X	X	X					

	Screening	Open-label phase 4 wks	Maintenance phase					Follow-up phase				
			Visit 1 ²⁾ Baseline	Visit 2 Randomisation	V3 to V14	V15	UNS/ Relapse FU visit ¹⁷⁾	Early Withdrawal	FU1 ^{18,20)}	FU2 ^{19,20)}	FU3 ²¹⁾	UNS FU ²²⁾
Frequency			Every 4 weeks (from V1 to V15) relative to V2								8 weeks after V15/EW	As needed
Visit window			±4 days (from V1 to V15)				No more than 7 days after subject calls		±2 days	±4 days	±4 days	≤ 7 days after call
Subject - Local safety and Tolerability			X	X	X	X	X	X				
Physician's Global Assessment of disease severity	X	X	X	X	X	X	X	X		X ²⁵⁾	X	
Selection of the target lesion/location		X										
Investigator's Assessment of the Severity of the target lesion/location		X	X	X	X	X	X	X		X ²⁵⁾	X	
Photographs of the target lesion/loc ^{11,13)}		X	X	X	X	X	X					
Local safety and Tolerability – Physician		X	X	X	X	X	X			X ²⁵⁾	X	
m-PASI		X	X	X	X	X	X			X ²⁵⁾	X	
BSA		X	X	X	X	X	X			X ²⁵⁾	X	
DLQI		X	X	X	X	X	X					
EQ-5D-5L		X	X	X	X	X	X					
WPAI:PSO		X	X	X ¹⁰⁾	X		X					

	Screening	Open-label phase 4 wks	Maintenance phase					Follow-up phase				
			Visit 1 ²⁾ Baseline	Visit 2 Randomisation	V3 to V14	V15	UNS/ Relapse FU visit ¹⁷⁾	Early Withdrawal	FU1 ^{18,20)}	FU2 ^{19,20)}	FU3 ²¹⁾	UNS FU ²²⁾
Frequency			Every 4 weeks (from V1 to V15) relative to V2								8 weeks after V15/EW	As needed
Visit window			±4 days (from V1 to V15)				No more than 7 days after subject calls		±2 days	±4 days	±4 days	≤ 7 days after call
Psoriasis symptom inventory			Daily during the open-label phase Weekly during the first 28 weeks of the maintenance phase and the 2 last weeks of the maintenance phase (for completers only)									
Compliance check ¹⁴⁾ -eDiary			Daily during the open-label phase Weekly during the maintenance phase (including relapse treatment)									
Subject treatment instructions			X	X			X					
Dispensing of IP			X	X	X		X ¹⁵⁾					
Return of IP				X	X	X	X ¹⁶⁾	X				
Drug compliance Form				X	X	X	X					
End of Trial Form								X			X	

1) A washout period of up to 4 weeks must be completed if the subject is treated or has recently been treated with anti-psoriatic treatments or other relevant medication, as defined by the exclusion criteria.

2) SV and Visit 1 can be performed at the same time for subjects who do not need a washout period.

3) Informed consent should be signed both by subject and (sub)investigator (medically qualified) before any trial related procedures are carried out. For subjects requiring a washout period, informed consent should be completed prior to washout.

4) Physical Examination at Visit 2 is required if the subject will not be randomised

5) Only applicable for women of child-bearing potential.

6) AEs will be collected from the date of signing the informed consent form i.e. during the washout period.

7) If albumin-corrected serum calcium is above the normal range, or if calcium:creatinine ratio is above the normal range and judged as clinically significant at this visit, sampling should be repeated at the following visit (Visit 3 or FU1)

8) If albumin-corrected serum calcium is above the normal range, or if calcium:creatinine ratio is above the normal range and judged as clinically significant at this visit, sampling should be repeated at a follow-up visit

9) Applicable only to subjects performing HPA axis assessments. ACTH challenge test should be performed at 8.00 a.m. \pm 30 min after checking vital signs and collecting blood and urine samples.

10) At Visit 8 (Week 28) only.

11) Only for subjects who consented for this procedure.

12) Or earlier in case of early withdrawal for subjects who have completed at least 40 weeks of the trial from baseline.

13) At designated sites.

14) Treatment compliance will be recorded by the subject in an eDiary.

15) In case of relapse, LEO 90100 will be dispensed at any unscheduled visit during the maintenance phase.

16) Subjects will have to return LEO 90100 dispensed during any unscheduled visit (UNS) at the following relapse follow-up visit (Relapse FU) or at the next regular 4-week visit.

17) Unscheduled visit (UNS) or relapse follow-up visit (Relapse FU) to be performed in case a relapse of psoriasis occurs (see figures section 6.1.4).

18) FU1 visit should only be performed if required, e.g. in case a non-serious AE is classified as possibly or probably related to the trial treatment or an SAE is on-going at the last on-treatment visit. Where the (sub)investigator considers it appropriate, the FU1 visit may be performed as a telephone contact. To be performed 2 weeks after the last on-treatment visit.

19) FU2 visit only applicable for subjects for whom the ACTH challenge test at end of treatment shows a serum cortisol concentration \leq 18 mcg/dl at both 30 minutes and 60 minutes after ACTH-challenge. The FU2 visit will be performed 4 weeks after the last on-treatment visit.

20) If both FU1 and FU2 are applicable (only applicable for subjects performing HPA axis assessments), only FU2 (4 weeks after the last on-treatment visit) will be performed. All assessments applicable at FU1 will be done at FU2.

21) Subjects will be followed up for 8 weeks after V15/EW for relapse/rebound evaluation. If the subject has not experienced a worsening of their psoriasis during the 8 week follow-up period, the FU3 contact may be conducted as a telephone contact, at the discretion of the investigator.

22) Subjects who experience a worsening of their psoriasis during the follow-up phase prior to the FU3 visit will contact the site as soon as possible for an unscheduled follow-up visit (section 6.1.5).

23) Subjects with a serum cortisol concentration \leq 18mcg/dl at both 30 minutes and 60 minutes after ACTH challenge at FU2 will be followed up until the adrenal suppression resolves. Further ACTH challenge tests must be captured in the UNS FU page in the eCRF.

24) If the subject withdraws prior to completing the initial open-label treatment phase, the ACTH-challenge test should not be performed.

25) Only required if last FU3 is performed at the trial site.

EW, early withdrawal; FU, follow-up; IP, investigational product; SV, screening visit; UNS, unscheduled visit; UNS FU, unscheduled follow-up visit; V, visit.

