6.1.4.1 Relapse at a regular 4-week (scheduled) visit

[figure not shown]
In case a relapse of psoriasis (defined as PGA of at least 'mild') is observed by the investigator at a regular monthly visit, the subject will be provided with rescue IP and instructed to apply it on the affected areas on trunk and limbs once daily for 4 weeks (all active psoriatic lesions including any new areas that become active during this 4-week treatment period).

Twice weekly maintenance treatment will continue unchanged on areas that are not active.

The subject will return to the trial site 4 weeks later to attend the regular monthly visit, where, if the subject is 'clear' or 'almost clear' according to PGA, maintenance treatment will be resumed on those areas. If the PGA of 'clear' or 'almost clear' is not achieved after 4 weeks of rescue treatment, the subject will exit the trial. For illustration, see Figure 2 below.

Figure 2 Relapse at a regular 4-week (scheduled) visit

6.1.4.2 Relapse between regular 4-week (scheduled) visits – more than one week prior to the next regular visit

If, in the opinion of the subject, a relapse of psoriasis occurs between regular visits when there is more than one week (7 days) to the next planned visit, the subject will contact the trial site to be assessed by the investigator at an unscheduled visit.

If relapse is confirmed by the investigator, the subject will be provided with rescue IP and instructed to apply it once daily for 4 weeks on any active psoriatic lesions on trunk and limbs during this time.

[figure not shown]
Twice weekly maintenance treatment will continue unchanged on areas that have not relapsed.

The subject will be examined at the next regular 4-week visit, but even if ‘clear’/‘almost clear’ at the regular visit, rescue treatment will continue. A relapse follow-up visit will take place at a relapse follow-up visit 4 weeks after the unscheduled visit where relapse treatment was initiated. If the subject is ‘clear’ or ‘almost clear’ according to PGA at this relapse follow-up visit, maintenance treatment on those areas will be resumed and the subject will follow the planned visit schedule.

If the subject is not ‘clear’ or ‘almost clear’ according to PGA after 4 weeks of relapse treatment, they will exit the trial. For illustration, see [Figure 3](#) below.

Figure 3 Relapse between regular 4-week (scheduled) visits – more than one week prior to the next regular visit

[figure not shown]

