6.1.5 Follow-up Phase

There are three types of follow-up visits, here listed in chronological order:

Follow-up Visit 1 (FU1):

A follow up visit 1 is only relevant for subjects with an ongoing AE at end of treatment. A follow-up visit/contact (FU1) should be conducted 14 (\pm 2) days after the last on-treatment visit (Visit 15/Early Withdrawal), unless the final outcome of the event, as defined below, has been determined before then.

This follow-up visit/contact (FU1) will take place only if:

1. there is an on-going SAE at the last on-treatment visit.
2. there is an on-going non-serious AE at the last on-treatment visit which is classified as possibly or probably related to the IPs
3. the albumin-corrected serum calcium is above the reference range at the last on-treatment visit
4. the calcium:creatinine ratio is above the reference range and clinically significant at the last on-treatment visit

Where the (sub)investigator considers it appropriate, the Follow-up Visit may be performed as a telephone contact. If a subject also is eligible for a follow up visit 2 (FU2), the follow-up on the ongoing AE can wait until FU2 (see below).

Follow-up Visit 2 (FU2):

For subjects undergoing the adrenocorticotropic hormone (ACTH) challenge test, a follow-up visit (Visit FU2) will take place 28 days after the ACTH challenge test performed at the end of treatment (Visit 15/Early Withdrawal) if the end of treatment test shows a serum cortisol concentration ≤ 18 mcg/dl at both 30 minutes and 60 minutes after ACTH challenge (39, 40).

If the results of the ACTH challenge test at Visit FU2 continue to show a serum cortisol concentration ≤ 18 mcg/dl at both 30 minutes and 60 minutes after ACTH challenge, further ACTH challenge tests should be performed, but not more often than at 4-weekly intervals, until the adrenal suppression resolves (i.e. serum cortisol concentration > 18 mcg/dl at 30 minutes or at 60 minutes after the ACTH-challenge, or at both time-points).

Refer to Section 8.12.1 for further details on the ACTH challenge test.

Follow-up visits should be performed within ± 4 days of the scheduled time; if they are outside this window, the (sub)investigator should record the reason in the subject's medical record but LEO do not need to be notified.

Follow-up Visit 3 (FU3):

All subjects should be followed up for events of rebound for 8 weeks after last application of IP. The different scenarios are outlined below:

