- Subjects who do not use rescue medication at Visit 15 will have a final contact (FU3) 8 weeks after Visit 15. Relapses confirmed at Visit 15 will be treated at the investigator's discretion; treatment with Enstilar[®] or IP is not allowed.
- Subjects who have completed 4 weeks of rescue treatment at Visit 15 (that is, Visit 15 is a relapse follow-up visit, see section 6.1.4.1) will have a final contact (FU3) 8 weeks after Visit 15.
- For subjects who use rescue medication at Visit 15 (that is, rescue medication was dispensed at an unscheduled visit after Visit 14 [see section 6.1.4.2]), the 8-week follow-up period will start after completion of the 4-week rescue treatment regimen (that is, at the relapse follow-up visit).

- Subjects who withdraw early from the trial, including subjects who leave the trial after the initial 4 weeks open-label treatment, will also have a follow-up visit (FU3) 8 weeks after their last IP application.

Subjects who experience rebound during the follow-up period prior to the FU3 visit will contact the site as soon as possible for an unscheduled follow-up visit (see below).

If the subject has not experienced a worsening of their psoriasis during the 8-week follow-up period, the FU3 contact may be conducted as a telephone contact, at the discretion of the investigator. If rebound is confirmed at the FU3 visit, the subject will be followed up for 14 days or until resolution (whichever occurs first). If the rebound is considered an SAE, the event must be followed up until a final outcome has been established, i.e. the follow-up may continue beyond the end of the clinical trial (see section [9.5](#)).

Rebound events in the follow-up period will be reported as (S)AEs in accordance with sections [9.2](#) and [9.4.1](#). See section [9.5](#) for the follow-up of related AEs during and after the trial.

Unscheduled follow-up visit

At the last treatment visit (Visit 15/Early Withdrawal), subjects should be instructed to contact the site if they experience a worsening of their psoriasis within the following 8 weeks to schedule a follow-up visit ('unscheduled follow-up'). The unscheduled follow-up visit should take place no more than 7 days after the initial contact.

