11.3.6.2 Rebound

Rebound will be defined as (i) an m-PASI ≥ 12 AND an increase in m-PASI of $\geq 125\%$ of the baseline value, or (ii) new pustular, erythrodermic or more inflammatory psoriasis either a) within 2 months after discontinuation of once-daily treatment in the initial open-label phase, b) within 2 months after discontinuation of once-daily relapse treatment, or c) within 2 months after end of maintenance treatment (up to Visit FU3)

Number of rebounds within two months after entering the maintenance phase will be summarised by treatment group in a table.

Number of rebounds occurring after the first two months of maintenance treatment (i.e. including the follow-up period) will be summarised by treatment group in another table.

Subjects with m-PASI $\geq 125\%$ of baseline (Visit1) score and cases of rebound will be listed.

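### For subjects on rescue at Visit 15, Table 4 times FU3 from Visit 15 but section 6.1.5 times it from the relapse follow-up visit, so a site using the table would hold FU3 too early

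*Protocol*

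**What the plan says.** Section 6.1.5 of the protocol sets a general rule for the last follow-up contact: "All subjects should be followed up for events of rebound for 8 weeks after last application of IP". It then lists scenarios. One is the subject whose rescue was dispensed at an unscheduled visit after Visit 14 and who is still using it at Visit 15. For that subject "the 8-week follow-up period will start after completion of the 4-week rescue treatment regimen", which the protocol equates with the relapse follow-up visit. Early withdrawals are timed from their last application.

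The schedule of procedures (section 8.1, Table 4) gives FU3 as "8 weeks after V15/EW". Footnote 21 repeats this: "Subjects will be followed up for 8 weeks after V15/EW for relapse/rebound evaluation". Neither mentions subjects on rescue at Visit 15.

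Section 6.1.5 also has subjects told, at Visit 15 or early withdrawal, to "contact the site if they experience a worsening of their psoriasis within the following 8 weeks".

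The rebound definition in section 11.3.6.2 includes events "b) within 2 months after discontinuation of once-daily relapse treatment". SAP section 5.5.4 uses the same window, and SAP Table 1 starts the follow-up phase on the day after the last application of maintenance or rescue product.

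**The concern.** Two current parts of the protocol give different FU3 dates for the same subjects. Section 6.1.5, the rebound definition and the SAP start the clock when treatment stops. Table 4 starts it at Visit 15, while these subjects are still applying once-daily drug.

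Incidence of rebound is a listed safety assessment (section 5.3), and these subjects have just finished a rescue course, which is the setting limb (b) of the definition is meant to observe. FU3 closes adverse event collection, rebound included (section 9.1), and it is the point up to which Enstilar is barred (section 16.2). If FU3 comes early, both end early. The 14-day extension in section 9.5 covers rebound confirmed at FU3 and related events already recorded. It does not look for a rebound that starts later.

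**Working it through.** This is visit-calendar arithmetic on nominal days.

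**The plan's own figure.** Section 6.1.4.3 gives a total duration of up to 64 weeks. Open-label 4 + maintenance 52 + follow-up 8 = 64 weeks, so the figure reproduces.

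**Inputs**
- Visits 14 and 15 are 28 days apart (Table 4).
- An unscheduled visit is used when a relapse occurs more than 7 days before the next planned visit (6.1.4.2).
- The relapse follow-up visit is "4 weeks after the unscheduled visit where relapse treatment was initiated" (6.1.4.2), so rescue lasts 28 days.
- FU3 is 56 days after its anchor.
- "Follow-up visits should be performed within ± 4 days of the scheduled time" (6.1.5); Table 4 gives FU3 the same window.

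**Steps.** Let d be the day of the unscheduled visit, counted from Visit 14.
1. Requiring 28 − d > 7 gives d = 1 to 20.
2. Rescue ends at Visit 14 + d + 28 = Visit 15 + d.
3. FU3 by Table 4 is at Visit 15 + 56, which is 56 − d days after rescue: 55 days at d = 1 and 36 days at d = 20.
4. FU3 by section 6.1.5 is at Visit 15 + d + 56, which is Visit 15 + 57 to Visit 15 + 76.
5. The shortfall is d days, from 1/56 = 1.8% to 20/56 = 35.7% of the 8 weeks.

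| d | Rescue ends | Table 4 FU3, days after rescue | 6.1.5 FU3 |
|---|---|---|---|
| 1 | Visit 15 + 1 | 55 | Visit 15 + 57 |
| 11 | Visit 15 + 11 | 45 | Visit 15 + 67 |
| 20 | Visit 15 + 20 | 36 | Visit 15 + 76 |

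**Visit window.** In days after Visit 15, the allowed range is [52, 60] by Table 4 and [52 + d, 60 + d] by section 6.1.5. The shortfall exceeds 4 days for d = 5 to 20 (16 of the 20 possible start days). The two ranges overlap only if 52 + d ≤ 60, so d ≤ 8. For d = 9 to 20 (12 start days) no single date meets both texts.

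**Limit of the range.** Step 1 applies the 7-day condition to the visit, whereas 6.1.4.2 applies it to the relapse. Table 4 allows the unscheduled visit up to 7 days after the call. A call on day 20 could lead to a visit on day 20 + 7 = 27, with Table 4's FU3 then only 56 − 27 = 29 days after rescue. So 20 days is the nominal figure and not a ceiling.

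**The case against.** The strongest reply is that the protocol already handles this case. Section 6.1.5 states the general rule, announces scenarios and gives this subgroup its own bullet. A specific rule is normally read over a summary cell, and footnote 22, next to the one at issue, refers to 6.1.5. Subjects must also attend the relapse follow-up visit, so the site sees them when their window opens. All of this stands, and it limits the harm to sites that schedule from Table 4 without going back to the bullet. It does not make the table right. Footnote 21 carries no reference to 6.1.5, and section 8.1 is where sites look for visit timing.

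A reader might infer that the Visit 15 contact instruction also ends adverse event collection and the Enstilar bar early. The documents do not support that: both are tied to FU3, and the instruction governs only calls the subject initiates. Elsewhere section 6.1.5 and footnote 22 ask subjects to call at any time before FU3. The phrase about the last treatment visit could even be read as the relapse follow-up visit, although its parenthesis names Visit 15. The instruction is a secondary mismatch that matters only for worsening late in the window.

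A reader might also take 12 of 20 or 16 of 20 as a share of subjects. They count possible start days, and the documents do not say how start days would be distributed or how many subjects would be involved.

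**Conclusion.** The conflict is real in the current text. For subjects dispensed rescue at an unscheduled visit between Visits 14 and 15, the FU3 row and footnote 21 contradict section 6.1.5, and 6.1.5 is the version that agrees with the rebound definition and the SAP. A site following Table 4 would hold FU3 about 1 to 20 nominal days too early, possibly more given the delay between call and visit. Rebound and adverse event collection and the Enstilar bar would then end before 8 weeks off once-daily drug.

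This rests on nominal visit spacing and on a site using the table over the bullet. The number of subjects is unknown. Power and the primary analysis are unaffected. It is a minor safety-schedule correction.

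It does not extend to FU1 or FU2, which recheck findings from the last on-treatment visit. Nor does it call for edits to section 7.8.3, which already points to 6.1.5 for the follow-up period, or to the stated total duration.

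**What to change.** In the Table 4 FU3 row and in footnote 21, write: *8 weeks after V15; for subjects on rescue at V15, 8 weeks after the relapse follow-up visit; for early withdrawals, 8 weeks after last IP application (see section 6.1.5)*. The early-withdrawal clause is needed because Table 4 counts from the withdrawal visit, whereas 6.1.5 counts from the last application, which may be earlier.

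In section 6.1.5, make the contact instruction run *until the FU3 visit*, and repeat it at the relapse follow-up visit.

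The cost is one table cell, one footnote and one sentence, plus a note to sites. It applies a rule the sponsor has already chosen, adds no visits or tests, and leaves FU1 and FU2 where they are.
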